7.8.2 Device Performance

A Device Performance analysis will be performed for ITT or As-Treated population to include:

- Deployment success defined as total number of patients with a successfully implanted Aortix Pump compared to the total number of patients within ITT population.
- Retrieval success defined as total number of patients with a successfully retrieved Aortix Pump compared to the total number of patients within the As-Treated population.
- Percentage of patients with ADS, ARS and pump device-related adverse events defined as the total number of patients with CEC-classified AEs of the corresponding category from the time of implant procedure through 30 days post-implant Follow-Up compared to the total number of patients in either the ITT population or As-Treated population as appropriate.

Descriptive summary will be provided for variables within Device Performance analysis. Corresponding listing will be provided for ITT population.

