3.2 Study Objectives

To evaluate the Aortix System, specifically to assess:

- Safety:
 - Observe the nature, severity, and frequency of adverse events associated with the delivery, use, and retrieval of the Aortix Pump.
- Performance:
 - Successfully deliver the Aortix Pump to the descending thoracic aorta using the Aortix Delivery System;
 - Aortix Pump shall function as programmed for the duration of therapy;
 - Manage the Aortix Pump Power Lead and access site over the course of therapy without significant complications;
 - Successfully retrieve and remove the Aortix Pump using the Aortix Retrieval System.
- Effectiveness:
 - Evaluate hemodynamic decongestion (CVP, PCWP) during Aortix therapy;
 - Evaluate the effect of the Aortix therapy on kidney function;
 - Evaluate the impact of the Aortix Pump on clinical biomarkers of congestion.

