3.3.2 Device Performance

1. Deployment (implant) and retrieval procedures success rates (rates will be calculated and reported)

2. Rate of occurrence of ADS, ARS and pump device-related adverse events (includes device malfunctions) (rate will be calculated and reported) [timeframe: implant attempt/implant to 30 day visit]

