4.4.2 Aortix Implant Procedure

Refer to the Aortix System Instructions for Use (PPL004) for all details of the Aortix Pump implant (deployment) technique, monitoring, management, and retrieval technique.

Anticoagulation should be initiated prior to the deployment of Aortix Pump in accordance with the Instructions for Use and **Appendix B: Anticoagulation Protocol**.

Ultrasound or another imaging modality should be used before and after implanting the pump to verify the femoral artery is not compromised (no vascular damage or clots).

Due to the potential for developing contrast induced nephropathy, if the use of iodinated contrast is required, then use the lowest dose possible and dilute 1:1 with saline.

Fluoroscopy should be used to aid in device placement and images of final device position should be captured and sent to Procyron.

If Aortix Pump is not positioned or functioning satisfactorily, the device may be repositioned or replaced as appropriate. After Aortix Pump implantation, anticoagulation should be maintained per **Appendix B**.

A fluoroscopic image of the final pump position should be taken, downloaded and the image documented. The image should be sent to Procyron.

During the procedure, patients should be monitored for any adverse events, including fever and anaphylaxis.

Any components of the Aortix Delivery System or Delivery Tool Kit that malfunction or are associated with an Adverse Event should be returned to the sponsor using the supplied Aortix Return Kit. Any device deficiencies should be reported.

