6.2 Adverse Event Definitions

Adverse Event (AE): Any untoward medical occurrence, unintended disease or injury, or untoward clinical signs (including abnormal laboratory findings) in participants, users, or other persons, whether or not related to the investigational medical device.

Note: This definition includes events related to the investigational medical device or the comparator. This definition includes events related to the procedures involved. For users or other persons, this definition is restricted to events related to investigational medical devices.

Adverse Device Effect (ADE): Adverse event related to the use of an investigational medical device.

Note: This definition includes adverse events resulting from insufficient or inadequate instructions for use, deployment, implantation, installation, or operation, or any malfunction of the investigational medical device. This definition includes any event resulting from use error or from intentional misuse of the investigational medical device.

Serious Adverse Event (SAE):

A Serious Adverse Event is an adverse event that:

- a. led to death
- b. led to serious deterioration in the health of the participant, that either resulted in:
 - a life-threatening illness or injury, or
 - a permanent impairment of a body structure or a body function, or
 - prolonged hospitalization, or
 - medical or surgical intervention to prevent life-threatening illness or injury or permanent impairment to a body structure of a body function

Note: Planned hospitalization for a pre-existing condition, or a procedure required by the Clinical Investigation Plan, without serious deterioration in health, is not considered a serious adverse event.

Serious Adverse Device Effect (SADE): An adverse device effect that has resulted in any of the consequences characteristic of a serious adverse event.

Device Deficiency: Inadequacy of a medical device with respect to its identity, quality, durability, reliability, safety, or performance.

Note: Device deficiencies include malfunctions, user errors, and inadequate labeling. They can be, but do not have to be, associated with an ADE or AE. Device deficiencies also include effects of electromagnetic interference (EMI). EMI effects can be intermittent; EMI related device effects, degradations, or malfunctions should be reported.

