5.2 Device Performance Endpoints

- Deployment and retrieval procedures success rates (rates will be calculated and reported);
- Rate of occurrence of ADS, ARS and pump device-related adverse events (includes device malfunctions) (rate will be calculated and reported) [timeframe: implant attempt/implant to 30 day visit].

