14.3.7.3	Boxplots of KCCQ Scores (As-Treated Population)
14.3.8.2	Boxplots of Dyspnea Score (As-Treated Population)

Listing Number	Listing Title
16.2.1.1	Listing of Screen Failure and Inclusion / Exclusion Criteria Assessment (All Enrolled)
16.2.1.2	Listing of Patient Disposition (All Enrolled)
16.2.2	Listing of Protocol Deviations (All Enrolled)
16.2.3	Listing of Analysis Populations (All Enrolled)
16.2.4.1	Listing of Patient Demographic and Baseline Characteristics (Intent-to-Treat Population)
16.2.4.2	Listing of Medical history (Intent-to-Treat Population)
16.2.4.3	Listing of Medications (Intent-to-Treat Population)
16.2.4.4	Listing of Furosemide Equivalents - Average Daily Dose (Diuretic Equivalents Analysis Population)
16.2.4.5	Listing of Inotropes Dosing Stages - Average Daily Dose (As-Treated Population)
16.2.5.1	Listing of Aortix Implant Procedure (Intent-to-Treat Population)
16.2.5.2	Listing of Aortix Retrieval Procedure (As-Treated Population)
16.2.5.3	Listing of Pump Speed Changes (Pump Speed Changes Population)
16.2.5.4	Listing of Device Deficiency (As-Treated Population)
16.2.6.1	Listing of Primary Safety (As-Treated Population)
16.2.6.2	Listing of Device Performance (Intent-to-Treat Population)
16.2.6.3	Listing of Primary Effectiveness (As-Treated Population)
16.2.6.4	Listing of Congestion Target (As-Treated Population)
16.2.7.1	Listing of CEC-classified Adverse Events (All Enrolled)
16.2.7.2	Listing of Investigator-classified Adverse Events (All Enrolled)
16.2.8.1	Listing of Urine Chemistry (As-Treated Population)
16.2.8.2	Listing of Blood Labs (As-Treated Population)
16.2.9	Listing of Vital Signs (As-Treated Population)
16.2.10.1	Listing of NYHA Classification (As-Treated Population)
16.2.10.2	Listing of Hemodynamics (As-Treated Population)
16.2.10.3	Listing of Cardiovascular Exam (As-Treated Population)
16.2.10.4	Listing of Echo (As-Treated Population)
16.2.10.5	Listing of Cardiac Output and Cardiac Power Output (As-Treated Population)
16.2.11.1	Listing of Dyspnea Evaluation (As-Treated Population)
16.2.11.2.1	Listing of Fluid Intake/ Urine Output (As-Treated Population)
16.2.11.2.2	Listing of Cumulative Fluid Intake, Urine Output and Net Loss (As-Treated Population)
16.2.11.2.3	Listing of Hourly rate of Fluid Intake / Urine Output / Net Loss (As-Treated Population)
16.2.12.1	Listing of EQ5D (As-Treated Population)
16.2.12.2	Listing of KCCQ (As-Treated Population)
16.2.13.1	Listing of Follow-up Information (As-Treated Population)

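### The device-performance rate is defined to include malfunctions, but SAP 7.8.2 counts only CEC-classified adverse events, so a malfunction without an adverse event enters no rate or summary table

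*SAP*

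**What the plan says.** - **Endpoint.** SAP 5.2 names it as "Rate of occurrence of ADS, ARS and pump device-related adverse events (includes device malfunctions", and protocol 3.3.2 uses the same wording. In both, the timeframe opens at the implant attempt.
- **Calculation.** SAP 7.8.2: "Percentage of patients with ADS, ARS and pump device-related adverse events defined as the total number of patients with CEC-classified AEs" of the corresponding category, "compared to the total number of patients in either the ITT population or As-Treated population as appropriate". Malfunctions are not mentioned here.
- **What a malfunction is.** Protocol 6.2 places malfunctions under device deficiencies and says of these: "They can be, but do not have to be, associated with an ADE or AE". Table 1 in protocol 6.1 gives device deficiencies their own reporting line, apart from AEs and adverse device effects.
- **What the CEC does.** Protocol 6.3 sets up the clinical events committee (CEC) to adjudicate adverse events. Device deficiencies are not named in its remit.
- **Outputs.** No table in SAP Appendix 1 is devoted to device deficiencies. Their one named output is Listing 16.2.5.4, "Listing of Device Deficiency (As-Treated Population". SAP 6.1.3 limits As-Treated to patients with the pump implanted; ITT (SAP 6.1.2) takes in every attempted implant.
- **Related objective.** Protocol 3.2 includes the performance objective "Aortix Pump shall function as programmed for the duration of therapy".

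**The concern.** The endpoint definition and the counting rule describe different sets of patients. The definition brings in malfunctions; the rule brings in only those that also led to an AE classified by the CEC. SAP 7.14, which records changes from the protocol, declares one change (to urine output) and not this one.

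The rate is the quantity in SAP 7.8.2 closest to the objective on pump function. Protocol 5.2 describes this as the first human use of the pump for longer than 90 minutes, and SAP 2.3 says the data will feed the design of later studies. A reader of the final report would take a low rate as covering malfunctions, because the endpoint says it does.

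**Working it through.** No stated figure is in dispute: SAP 2.3 says the sample size was not statistically derived, and no target is set for this rate. The check is first one of text, then an illustration of size.

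**Where an AE-free malfunction goes**

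| Output | Implanted patient | Aborted implant |
|---|---|---|
| Device-related AE rate, SAP 7.8.2 | not counted | not counted |
| Table of device deficiencies | none planned | none planned |
| Listing 16.2.5.4 (As-Treated) | listed | absent |
| Deployment success (ITT denominator) | counted as success | counted as failure, cause not given |
| Retrieval success (As-Treated denominator) | affected only if retrieval fails | not applicable |
| Listings of implant procedure and of device performance (ITT) | patient included | patient included |

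**Size, on assumed counts**

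Inputs: 30 implanted patients (SAP 2.3). Assumed, since the documents give no malfunction rate: *h* implanted patients with an AE-free malfunction and *a* implants aborted by an AE-free delivery-system malfunction, each from 0 to 5, in different patients, with no other failed attempts and no other device-related AE.

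- ITT size: *n* = 30 + *a*
- Rate under SAP 7.8.2, ITT denominator: 0/*n*
- Rate with malfunctions counted: (*h* + *a*)/*n*
- Deployment success: 30/*n*
- Exact (Clopper-Pearson) 95% limits for *k* of *n*: the 0.025 quantile of Beta(*k*, *n* − *k* + 1) and the 0.975 quantile of Beta(*k* + 1, *n* − *k*); the lower limit is 0 when *k* = 0.

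| *h* | *a* | SAP 7.8.2 rate (95% CI) | Malfunctions counted (95% CI) | Deployment success | Shown in Listing 16.2.5.4 |
|---|---|---|---|---|---|
| 0 | 0 | 0/30 = 0% (0 to 11.6) | 0/30 = 0% (0 to 11.6) | 30/30 = 100% | 0 of 0 |
| 1 | 0 | 0/30 = 0% (0 to 11.6) | 1/30 = 3.3% (0.1 to 17.2) | 30/30 = 100% | 1 of 1 |
| 3 | 0 | 0/30 = 0% (0 to 11.6) | 3/30 = 10.0% (2.1 to 26.5) | 30/30 = 100% | 3 of 3 |
| 0 | 3 | 0/33 = 0% (0 to 10.6) | 3/33 = 9.1% (1.9 to 24.3) | 30/33 = 90.9% | 0 of 3 |
| 3 | 3 | 0/33 = 0% (0 to 10.6) | 6/33 = 18.2% (7.0 to 35.5) | 30/33 = 90.9% | 3 of 6 |
| 5 | 5 | 0/35 = 0% (0 to 10.0) | 10/35 = 28.6% (14.6 to 46.3) | 30/35 = 85.7% | 5 of 10 |

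The rate under SAP 7.8.2 stays at 0% throughout. Malfunctions in implanted patients can be read from the listing; those in aborted implants lower deployment success but are not in the listing.

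**The case against.** **The SAP may not mean to exclude malfunctions.** SAP 5.2 keeps the parenthesis, and the reference in 7.8.2 to the corresponding category can be read together with it. Device failure and malfunction are on the risk list in protocol 5.2, and protocol 6 lets the CEC add to the definitions, so the committee could code malfunctions as AEs. The CEC charter and the CRF are not among the documents. This stands as a possibility, but it rests on a discretionary choice that the SAP does not state.

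**The parenthesis might cover only AEs caused by malfunctions.** The definition of an adverse device effect in protocol 6.2 already covers those, so the parenthesis would add nothing. If that is the intent, the SAP should say so.

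**The pilot relies on patient-level review.** Protocol 7 puts individual review of patients first, and SAP 3.1 promises that all study data will be listed. Faults in implanted patients are therefore not hidden. This includes a patient whose pump was exchanged under protocol 4.4.2 ("If Aortix Pump is not positioned or functioning satisfactorily, the device may be repositioned or replaced as appropriate"), provided that the deficiency was reported. This stands, and it limits the point to the rate, the missing table and the population of the listing.

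**The counts in the illustration are invented.** They are, and the first-in-human study in protocol 1.2 reports no device failures. But that study had 6 patients and an average of 70 minutes of pump operation. Zero of 6 has an exact upper 95% limit of 1 − 0.025^(1/6) = 45.9%, so it says little about reliability over days.

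**Stronger readings that the documents do not support.**

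- A reader might infer that implants aborted by a delivery-system fault go uncounted. They do not: each lowers deployment success over ITT, and the patient is in the ITT implant-procedure listing.
- A reader might infer that the performance objective could be declared met on a 0% rate. No threshold or test is set; the rates are only calculated and reported.
- A reader might infer that the plan must also score the Control System, each pump opened, or uninterrupted running at programmed speed. Both documents limit the endpoint to ADS, ARS and pump. Appendix A of the protocol shows no data item for uninterrupted running or for pumps opened per patient. Nothing stated keeps Control System deficiencies out of the listing.

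**Conclusion.** The point holds. Followed as written, SAP 7.8.2 yields a rate narrower than the endpoint in protocol 3.3.2 and SAP 5.2, and SAP 7.14 does not declare the difference. An AE-free malfunction enters no rate or summary table. In an aborted implant it is also missing from the one deficiency listing, although the endpoint's timeframe starts at the attempt; what is lost there is the attribution to a device malfunction, not the failed deployment.

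Each omitted implanted patient is worth 1/30 = 3.3 percentage points when ITT is 30. Over the assumed range (*h* and *a* each 0 to 5), the rate with malfunctions counted runs from 0% to 28.6% while 7.8.2 gives 0%. The true gap is unknown and may be nil. The conclusion assumes that the CEC does not classify AE-free malfunctions as AEs, which the documents neither require nor rule out. The endpoint is descriptive, so no decision rule is affected, but the definition and the calculation should be made to agree.

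**What to change.** In SAP 7.8.2:

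1. Define the numerator as patients with a CEC-classified device-related AE **or** a reported malfunction (device deficiency) of the ADS, ARS or pump, each patient counted once.
2. Show the two parts separately, and by ADS, ARS and pump.
3. Replace the open choice of population with a stated one: ITT for the ADS and for the overall rate, As-Treated for the ARS. State the pump's as well; ITT would fit the timeframe, since the pump comes preloaded in the delivery system.
4. Change Listing 16.2.5.4 to the ITT population.

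If AE-free malfunctions are meant to stay out, the alternative is to correct the endpoint wording in SAP 5.2 and record the change in SAP 7.14.

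Cost: SAP wording, one more table, and possibly a less favourable descriptive rate. Device deficiencies are already reported to the sponsor (protocol 4.4.2 and Table 1 in 6.1), so the main change needs no new collection. A per-pump success rate, a measure of uninterrupted running at programmed speed, and inclusion of the Control System are optional; before adding any of them, check that the data are collected.

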7.8.3 Primary Effectiveness

Primary Effectiveness analysis will be performed for As-Treated population to include:

- Percentage of patients with clinically significant decongestion as measured by the PA catheter compared to the total number of patients in the As-Treated population;
- Percentage of patients with a decrease in CVP or PCWP of $\geq 20\%$ from pre-implant until congestion target is met or therapy deemed ineffective compared to the total number of patients in the As-Treated population;
- Change in Urine Output Assessed as the hourly rate of urine output before pump placed vs hourly rate of urine output over the Aortix therapy period until either congestion target met or therapy is deemed ineffective for patients within As-Treated population;
- Percentage of patients with a decrease in BNP or NT-pro-BNP of $\geq 20\%$ from pre-implant until congestion target is met or therapy deemed ineffective with respect to the total number of patients within the As-Treated population.

Descriptive summary of percentages will be provided for device performance analysis variables. Corresponding listings will be provided for As-Treated populations.

In addition, effectiveness measurements (CVP, PCWP, BNP and NT-pro-BNP) collected Day of Implant (Pre-implant) and Once Congestion Target Met will be compared using non-parametric Wilcoxon Signed-Rank by subgroup and overall for those patients within As-Treated populations that have the effectiveness measurements available at both timepoints.

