3.3.3 Primary Effectiveness Endpoints

1. Clinically significant decongestion as measured by the PA catheter. Decrease in CVP or PCWP of $\geq 20\%$. [timeframe: pre-implant vs when congestion target is met or therapy deemed ineffective].
2. Change in Urine Output Assessed as the hourly rate of urine output before pump implanted vs hourly rate of urine output over the Aortix therapy period (until congestion target met or therapy deemed ineffective)
3. Decrease in BNP or NT-pro-BNP by 20% (pre-implant vs when congestion target is met or therapy deemed ineffective)

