4.3 Baseline Monitoring

Once patient is enrolled, baseline monitoring will begin. The following shall be done:

- Collect a medical history
- Perform a cardiovascular exam
- Collect vital signs (heart rate-HR, blood pressure-BP, respiratory rate-RR), NYHA classification, height
- Administer KCCQ and EQ5D assessments
- Collect baseline blood labs (See **Appendix A**).
- Echocardiogram (for the baseline echocardiogram, an echocardiogram taken during the current hospitalization may be used if the required parameters are recorded and no clinically significant changes are suspected from time of the echocardiogram to the baseline visit)

Echocardiogram parameters to be recorded: severity of AR, TR and MR, EF, LVESV, LVEDV, LVEDD, LVESD, CO, SV, LA diameter, TAPSE, and RVIDD. The selection of the echocardiogram technique and views are left to the

^x If the patient has had imaging within the last 12 months, this can be used in lieu of repeating the imaging if no clinically significant change is suspected.

institution. A report should be generated and kept as source documentation. Baseline assessments will be made in accordance with the schedule of assessments in **Appendix A**.

In addition to baseline monitoring, the following shall be done:

- Urinary collection device placement at least 12 prior to implant
 - Begin careful fluid intake and output (I/O) monitoring starting at least 6 hours prior to Aortix implant)
- Document current renal and cardiovascular medications
 - Cease to adjust diuretics and inotropes 12 hours prior to Aortix implant

The following categories of medications should be recorded, at a minimum: ACE inhibitor, ARNI, angiotensin receptor blocker, antiarrhythmic, beta blocker, digoxin, diuretic, inotrope, nitrate, MRA, SGLT2, thiazide diuretic, nitroprusside. Medication dose changes will be tracked through the 72 hour/discharge visit. Medications at the follow-up will also be recorded.

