After signing informed consent, a urinary collection device will be placed, if not already present. A Foley catheter is recommended, but an external urine collection device may be used per institution requirements. The urine collection device will be placed (do not measure the urine collected during catheter placement) at least twelve (12 hours) before the Aortix Pump placement. If a urinary collection device is already in place, urine should be discarded. Output and intake should be strictly observed starting twelve hours prior to the scheduled implant. The urine collection device and the strict ins/outs monitoring will continue until the Aortix pump is retrieved. The first measurement of intake and output should occur at least six hours prior to Aortix placement and should be recorded every two hours until the pump is turned on. Measurements will occur at the frequency outlined in **Appendix A**.

Fluid ins should be monitored (IV and Oral) for the entire duration the urine collection device is in place with final measurements taken at the time of device retrieval.

Patients will receive standard medical therapy throughout the study. Patients should be on optimized medical therapy prior to being considered for Aortix Pump placement. To characterize the effect of the experimental device, physicians should not adjust the diuretic or inotrope dosing regimen during the twelve (12) hours prior to or the twelve (12) hours after Aortix Pump placement, unless medically necessary. **Diuretics and inotropes should not be adjusted for twelve (12) hours after the Aortix pump is turned on, however, after that point, while the Aortix pump is running, cessation of medications or down titration of diuretics, inotropes or other medications are allowed.** Adjustments of medical therapy can otherwise be made at any point during the study period at the discretion of the treating physician. All medications and medications adjustments will be captured on eCRFs.

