4.5 Aortix Post-Deployment Monitoring and Management

The Aortix Pump has been tested to operate safely for 7 days of use. Aortix therapy should continue until objective signs of hemodynamic congestion have resolved, alternative / escalated therapy is required, or if device related safety concerns arise. The duration of Aortix pump use should be dictated by the physician's target for diuresis (net fluid and weight loss). In addition, the pre-specified target for pump effectiveness is a **minimum 20%** decrease in the patient's CVP and PCWP from pre-implant. **Diuretics and inotropes should not be adjusted for twelve (12) hours after the Aortix pump is turned on. After that point, while the Aortix pump is running, cessation of medications or down titration of diuretics, inotropes or other heart failure medications are allowed.** Adjustments of other medical therapy can otherwise be made at any point during the study period at the discretion of the treating physician. All medications and medications adjustments will be captured on eCRFs.

Refer to the Aortix System Instructions for Use (PPL004) for details of the Aortix Pump management.

If clinically significant device migration is suspected, use x-ray or another imaging modality to verify pump position.

It is recommended that the patient's vital signs be monitored frequently post procedurally (e.g., vitals checked every 15 minutes for the first hour, then every 30 minutes for the second hour). The patient's pedal pulses should be monitored post procedurally frequently for distal limb perfusion, ideally but not limited to, every fifteen (15) minutes times four (4), every thirty (30) minutes times two (2) and every hour (1) for two (2) hours and then as frequently as signs and symptoms warrant. In addition, the access site should be monitored for bleeding, hematoma, swelling or signs of infection.

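### The CVP/PCWP responder rate counts a 20% fall whatever therapy was added before the reading, and even when the reading was taken because pump therapy was judged ineffective

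*SAP*

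**What the plan says.** **The endpoint.** Protocol 3.3.3 lists first among the primary effectiveness endpoints: "Clinically significant decongestion as measured by the PA catheter. Decrease in CVP or PCWP of" at least 20%, with "timeframe: pre-implant vs when congestion target is met or therapy deemed ineffective". SAP 7.8.3 turns this into a percentage of patients with such a fall "from pre-implant until congestion target is met or therapy deemed ineffective compared to the total number of patients in the As-Treated population". The As-Treated set (SAP 6.1.3) is everyone with the pump implanted. Neither added therapy nor the reason for the reading enters that definition.

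**The pump target.** Protocol 4.5 sets the target for pump effectiveness as a minimum 20% "decrease in the patient's CVP and PCWP from pre-implant". The target needs both pressures; the endpoint needs one.

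**When the reading is taken.** Protocol 4.5.3 and Appendix A place it once the target is met or therapy is judged ineffective, before weaning and within 12 hours of its start. Among the reasons to end therapy, Protocol 4.5 names the case where "alternative / escalated therapy is required, or if device related safety concerns arise".

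**What else may be given.** Protocol 4.3 holds diuretics and inotropes constant for 12 hours either side of implant unless medically necessary. After that it names only stopping or reducing them, or other medications, while the pump runs. It then adds: "Adjustments of medical therapy can otherwise be made at any point during the study period at the discretion of the treating physician". Protocol 4.5 differs on two counts: its stop-or-reduce sentence refers to other heart failure medications, and its free-adjustment sentence is limited to other medical therapy. The drugs recorded include "inotrope, nitrate, MRA, SGLT2, thiazide diuretic, nitroprusside".

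**Renal replacement.** Ultrafiltration, CRRT and dialysis are terminal events after which a patient may, but need not, be withdrawn (Protocol 3.6). Their use is reported as additional data (SAP 5.4).

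**The concern.** The rate is labelled as clinically significant decongestion, but the scoring rule is silent on two things that decide what a fall in pressure means.

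The first is why the reading was taken. A patient whose therapy was judged ineffective is scored by the same rule as one who met the target, and one pressure out of two is enough.

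The second is what was given in between. A fall after a vasodilator was started, or after an inotrope or diuretic was increased, counts in the same way as a fall on an unchanged regimen.

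In a randomised trial a control arm would absorb part of this. Here there is none, and the study is meant to supply initial evidence of effectiveness and input to later designs (Protocol 7, SAP 2.3). A later trial planned on this rate would inherit whatever share of it the pump did not produce.

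**Working it through.** **1. Is there a planned figure to reproduce?** Not for this endpoint. No target rate, alpha, power or margin is stated, and the 30 implanted patients were not statistically derived (SAP 2.3). What follows is a reading of the text plus an assumption range.

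**2. Does the text let a judged failure be a responder?** Yes, directly. The reading point in Protocol 3.3.3 and SAP 7.8.3 includes the case where therapy is judged ineffective, and the only further condition is the 20% fall. The gap between either pressure (endpoint) and both pressures (Protocol 4.5 target) makes it easy to miss the target and still be scored a responder.

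**3. Does any passage link added therapy to responder status?** I found none.
- SAP 6.1.3: no such criterion, and SAP 6.1 has no per-protocol set.
- SAP 7.4.2: change in furosemide equivalents, tabulated separately.
- SAP 7.4.3: a category for patients whose inotrope stage increased, tabulated separately.
- SAP 5.4: use of CRRT, ultrafiltration and dialysis, as additional data.
- Protocol 4.5.3: the reading must precede weaning. It need not precede added therapy.
- SAP 7.8.3: no sensitivity analysis of the responder rate.

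**4. What is one patient worth?** With the denominator fixed at 30, 1/30 = 3.3 points. If 21/30 were responders under the present rule (assumed), the rate would be 70.0%, exact 95% CI 50.6 to 85.3. Reclassifying k responders gives:

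| k | Rate | Exact 95% CI |
|---|---|---|
| 1 | 20/30 = 66.7% | 47.2 to 82.7 |
| 3 | 18/30 = 60.0% | 40.6 to 77.3 |
| 6 | 15/30 = 50.0% | 31.3 to 68.7 |

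The documents give neither the starting count nor k.

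**5. How often does chance alone give a response?** All inputs except the eligibility rule and the 20% cut are assumptions:
- true CVP mean 10 to 15 mmHg, SD 5;
- true PCWP mean 18 to 25 mmHg, SD 6, correlation 0.5;
- within-patient SD 1.5 to 2.5 mmHg (CVP) and 2 to 4 mmHg (PCWP);
- selection on PCWP of at least 20 or CVP of at least 12 mmHg (inclusion criterion 3);
- no true change between the two readings.

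A response is a second reading at or below 0.8 times the first.

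| Means CVP/PCWP | SDs CVP/PCWP | Fall in either | Fall in both |
|---|---|---|---|
| 15/25 | 1.5/2 | 10% | 0.3% |
| 12/22 | 2/3 | 28% | 2.5% |
| 10/18 | 2.5/4 | 45% | 7% |

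If 6 of 30 patients were judged ineffective (assumed) and had no true change, the expected number scored as responders is 6 × 0.10 = 0.6 to 6 × 0.45 = 2.7, or 2 to 9 points. This measures reading-to-reading noise only. It says nothing about how often therapy is added or what that does to the pressures.

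**The case against.** The strongest case against runs as follows.

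**The drug rules are tighter than a quick reading suggests.** After 12 hours both sections name only stopping or reducing diuretics and inotropes. The Protocol 4.5 wording may extend that to nitrates and nitroprusside as heart failure medications. A reader might infer that these drugs can be started or raised freely throughout; the documents do not settle that. This stands. It narrows the route without closing it: the free-adjustment sentence quoted from Protocol 4.3 is broader, and SAP 7.4.3 provides for increased inotrope stages.

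**Sequence protects the reading.** If "alternative / escalated therapy is required", that is a reason to end pump therapy, and the reading is due before weaning. Ultrafiltration before the reading should therefore not be treated as the ordinary path. This mostly stands, but no passage requires the order.

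**The data are there.** A reader might infer that a fall due to other treatment could never be recognised later. That is not so: medication changes are recorded to 72 hours or discharge, the SAP lists medications and effectiveness by patient, and Protocol 7 has each patient reviewed individually. This stands in full, but individual review does not correct the reported percentage.

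**A judged failure may still have a real fall.** Duration of use depends on the physician's diuresis target, so therapy can fail on diuresis while one pressure truly falls. Keeping such patients in the denominator is right, and the SAP never calls the rate device success. Counting regardless of other therapy is also a recognised treatment-policy choice. This stands as a reason to keep the present rate, but the SAP does not state that it is making that choice.

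**Conclusion.** The point holds in a limited form. SAP 7.8.3 counts a 20% fall in either pressure whatever therapy was added and whatever prompted the reading. In patients with added therapy, or with therapy judged ineffective, an uncontrolled rate cannot be attributed to the pump.

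The wording establishes this; the frequency is unknown. The effect is 3.3 points per reclassified patient out of 30. The chance range of about 10% to 45% depends entirely on the assumed means and SDs. The documents do not support a claim that the rate is inflated by any particular amount, or that rescued patients are routinely counted.

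There is no success threshold or alpha to breach, so this is minor to moderate: worth fixing because it is cheap and bears on what the first effectiveness endpoint can support.

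**What to change.** Keep the present rate and state that it counts patients regardless of added therapy and of the reason for the reading. Add to SAP 7.8.3:

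> Supplementary responder rate, As-Treated denominator, same single pre-weaning reading as the main rate. A patient is a responder only if (a) the fall of at least 20% is present at that reading; (b) therapy had not been deemed ineffective; and (c) between pump start and that reading there was no start of, or increase above the pre-implant regimen in, an inotrope, nitrate/nitroprusside or diuretic, and no ultrafiltration, CRRT, dialysis or other mechanical circulatory support. All others are non-responders. The same rule applies to BNP/NT-pro-BNP.

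The single reading matters. Crediting any fall reached before added therapy would let every serial reading count. With 7 CVP and 4 PCWP readings (the Appendix A schedule over 72 hours) and the assumptions above, false response would rise from about 10-45% to about 34-84%.

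Three further items:
- Report both rates by reason for the reading, where the CRF or Listing 16.2.6.4 (Congestion Target) records it.
- State which reading is used for CVP/PCWP and BNP. SAP 7.14 says the target-met timepoint is not collected in the latest CRF, but names a substitute only for urine output.
- Reconcile Protocol 4.3 with 4.5 on which drug adjustments are allowed after 12 hours, and Protocol 3.3.3 and SAP 7.8.3 with Protocol 4.5 on either pressure versus both. Which clinical rule is right is not judged here.

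The cost is SAP wording and a small derivation from recorded medication and event data, subject to confirming that the CRF captures when therapy was deemed ineffective. The supplementary rate can only equal or fall below the present one. Patient care is unchanged.
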